6.6 PHARMACOKINETIC ANALYSES

As outlined in [Appendix 3](#), plasma PK samples will be obtained for GDC-0810 *and plasma concentrations will be summarized by visit*. Population PK analysis *may* be performed to characterize the PK in this study. Additionally, population PK/PD analysis may be performed to assess potential correlations of exposure with dose, demographics, PD, safety, and efficacy outcomes. The results of these population analyses may be reported separately from the clinical study report.

6.7 PATIENT-REPORTED OUTCOME ANALYSES

The percentage of participants randomized to each treatment group who complete each measure at baseline and each subsequent assessment point (i.e., PRO completion rates) will be calculated and compared. Summary statistics (mean, standard deviation, median, and range) of absolute scores and the change from baseline will be reported for all items and subscales of the EORTC QLQ-C30 and QLQ-BR23 according to the EORTC scoring manual ([Fayers et al. 2001](#)). Descriptive statistics (means) will be used to display the results of the modified version of the TSQM subscales (side effects, convenience, and global satisfaction), and responses obtained while receiving

GDC-0810 treatment will be compared to responses obtained to patients receiving fulvestrant (Atkinson et al. 2004).

In the event of incomplete data, if the scale has more than 50% of the constituent items completed, a pro-rated score will be computed consistent with the scoring manuals and validation papers of the measure. For subscales with less than 50% of the items completed, the subscale will be considered missing.

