4.2 METHOD OF TREATMENT ASSIGNMENT

After written informed consent has been obtained and eligibility has been established and approved, the study site will obtain the patient's identification number and treatment assignment from the Interactive Web Response System (IWRS). Patients will be randomized to receive either GDC-0810 or fulvestrant in an approximate 1:1 ratio through the use of a permuted block randomization method.

Randomization will be stratified by the following criteria:

- Visceral versus non-visceral disease:
 - Visceral disease: metastatic disease in the lung, liver, adrenal glands, brain, heart, pericardium, pleura, peritoneum, or other organs of the chest, abdomen and pelvis
 - Non-visceral disease: absence of metastatic disease in visceral organs. Pleural effusions and/or ascites. Disease involving lymph nodes and disease involving bone are not considered to be visceral disease.

- Geographical region:
 - United States
 - European Union
 - Rest of World (remaining countries)

The Sponsor, the investigators, and the patients will be unblinded to treatment assignment.

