4.5.8 Patient-Reported Outcomes

With the initiation of protocol amendment version 2, patient-reported outcomes will no longer be collected.

The EORTC QLQ-C30, QLQ-BR23, and a modified version of the TSQM will be collected to more fully characterize the clinical profile of GDC-0810 and fulvestrant.

The EORTC QLQ-C30 (see [Appendix 4](#)) and the QLQ-BR23 (see [Appendix 5](#)) are validated and reliable self-report measures ([Aaronson et al. 1993](#); [Sprangers et al. 1996](#); [Osoba et al. 1997](#)). The EORTC QLQ-C30 (version 3) consists of 30 questions that assess the following: global health status/HRQoL, five aspects of patient functioning (physical, emotional, role, cognitive, and social); three symptom scales (fatigue, nausea and vomiting, and pain); and six single items (dyspnea, insomnia, appetite loss, constipation, diarrhea, and financial difficulties) with a recall period of “the last week.” The EORTC QLQ-BR23 breast cancer module also uses a recall period of “the past

week,” and consists of 23 additional items assessing disease/treatment symptoms (systemic therapy side effects, breast symptoms, arm symptoms, and hair loss) and aspects of patient functioning (body image, sexual functioning, and future perspective).

The modified version of the TSQM (see [Appendix 6](#)) is a validated instrument consisting of 11 questions that measure patients’ satisfaction with medication. The 11 items incorporate 3 domains: side effects, convenience, and global satisfaction. The original version of the TSQM also contains a three-item subscale of effectiveness of treatment. The original TSQM had not previously been used in a cancer population, and during a validation study, cancer patients clearly indicated that they were not able to interpret or respond to the items on the effectiveness subscale.

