The PRO instruments will be translated as required in the local language and completed in their entirety by the patient. To ensure instrument validity and that data standards meet health authority requirements, PRO questionnaires scheduled for administration during a clinic visit must be completed by the patient at the investigational site at the start of the clinic visit prior to other study assessments and before administration of study treatment. Interviewer assessment is allowed, but can only be conducted by a member of the clinic staff, if the patient is unable to complete the measure on their own. Study personnel should review all questionnaires for completeness before the patient leaves the investigational site.

An electronic PRO (ePRO) data collection modality will be employed. To capture PRO data during study treatment, patients will complete the questionnaires on a validated ePRO tablet at the site. The ePRO device and instructions for completing the PRO questionnaires electronically will be provided by the investigator staff. The data will be transmitted via a pre-specified transmission method (e.g., Web or wireless) automatically after entry to a centralized database at the ePRO vendor. The data can be accessed securely by appropriate study personnel via the Internet.

Please see [Appendix 1](#) for the schedule of PRO assessments. It should take approximately 10 minutes to complete the PRO assessments at each timepoint.

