4.6.2 Study Drug Discontinuation

Patients must discontinue study drug if they experience any of the following:

- Any medical condition that the investigator or Sponsor determines may jeopardize the patient's safety if the patient continues to receive study drug
- Pregnancy
- Documented disease progression or relapse
- Unacceptable toxicity
- Use of another anti-cancer therapy
- Patient or investigator decision

The primary reason for study treatment discontinuation should be documented on the appropriate eCRF. Patients who discontinue study treatment prematurely will not be replaced.

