6.1 DETERMINATION OF SAMPLE SIZE

The trial is designed to evaluate the clinical activity and safety of GDC-0810 compared with fulvestrant in patients with ER-positive locally advanced or MBC. It is for hypothesis generation, and is not powered to detect minimum clinically meaningful difference between treatment arms.

A total of approximately 152 patients will be enrolled in this study. It is assumed that the median duration of PFS in the fulvestrant control arm is 5.5 months and 8.5 months in the GDC-0810 arm. The final analysis of all randomized patients will be triggered by the occurrence of approximately 95 PFS events, which is expected to occur 26 months after the first patient is randomized. [Table 4](#) shows expected probabilities of observing a hazard ratio of less than 0.5, 0.6 and 0.7 in the final analysis in all randomized patients under varying assumptions for the true underlying hazard ratio. Note that formal hypothesis testing is limited. Rather than testing treatment differences at a statistically significant type I error level of 5%, 90% confidence intervals (CI) for the hazard ratio will be calculated.

At a target hazard ratio of 0.6, the corresponding 90% CI based on 95 PFS events is (0.43, 0.84) which is considered to provide meaningful precision.

Table 4 Expected Probability of Observing a Hazard Ratio of <0.5, <0.6, or <0.7 in the Final Analysis (All Patients)

True HR	95 PFS Events in ITT Population		
	Observed HR < 0.50	Observed HR < 0.60	Observed HR < 0.70
0.4	0.86	0.98	0.99
0.5	0.50	0.81	0.95
0.6	0.19	0.50	0.77
0.7	0.05	0.23	0.50
0.8	0.01	0.08	0.26

HR=hazard ratio; ITT=intent to treat; PFS=progression-free survival.

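### Section 6.7 compares PRO completion over all randomized patients at every assessment, so post-baseline rates mix compliance with time on treatment and can differ between arms when every form due is completed

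*Combined protocol and SAP*

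**What the plan says.** Section 6.7 takes as its completion measure "The percentage of participants randomized to each treatment group who complete each measure at baseline and each subsequent assessment point", and the sentence continues: "i.e., PRO completion rates) will be calculated and compared". The stated base is everyone randomized to the arm, at baseline and at every later assessment. Neither section 6.7 nor any other section defines a second rate among patients who were due a form.

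Three other provisions determine who can be asked for a form:

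- Section 4.5.8 describes collection on treatment: "To capture PRO data during study treatment, patients will complete the questionnaires on a validated ePRO tablet at the site".
- Section 4.6.2 lists among the mandatory reasons to stop study drug: "Documented disease progression or relapse".
- Section 4.5.8 also states: "With the initiation of protocol amendment version 2, patient-reported outcomes will no longer be collected". Section 3.3.10 says the same in other words, while section 3.1 lets patients with clinical benefit stay on treatment. Section 6.7 was not adapted to this stop.

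The design assumption on time to progression is in section 6.1: "It is assumed that the median duration of PFS in the fulvestrant control arm is 5.5 months and 8.5 months in the GDC-0810 arm".

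**The concern.** A completion rate is useful because it shows whether patients who should have answered did answer. Here the base includes patients whom the protocol no longer asks: those off treatment after progression, those who have died and, read literally, those still on treatment after Version 2. A fall in the rate could then reflect missed questionnaires, progression or the amendment, and the percentage alone cannot separate them.

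This matters most for the comparison between arms. Completion is the only check in section 6.7 on whole missing questionnaires; the 50% rule there deals with missing items within a scale. A reader needs that check to judge the change-from-baseline summaries and the TSQM comparison. The trial is open-label, and section 3.3.4 acknowledges possible bias from patients knowing their treatment, so unequal non-response is a fair question. If time on treatment differs between arms, the stated rate can show a gap without any non-response, or hide or reverse a real one.

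**Working it through.** The plan states no expected completion rate, so it has no figure of its own to reproduce on this point. The check asks what the stated rate would show if every form due were completed.

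**Inputs**

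- Median PFS: 5.5 months on fulvestrant and 8.5 months on GDC-0810 (section 6.1). With exponential PFS the hazard ratio is 5.5/8.5 = 0.647.
- Sample size: "A total of approximately 152 patients will be enrolled in this study" (section 6.1), allocated "in an approximate 1:1 ratio through the use of a permuted block randomization method" (section 4.2), so about 152/2 = 76 per arm.
- Enrollment of about 22 months (synopsis, Length of Study).

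**Assumptions that the documents do not give**

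- PFS is exponential and stands in for time on treatment.
- Visit times are illustrative. Section 4.5.8 refers to Appendix 1 for the PRO schedule, but Appendices 1 and 2 now carry no PRO row. Day 1 of a cycle is used here.
- For the Version 2 step only: uniform accrual, and a stop between 12 and 26 months after the first patient.

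**Step 1. Identity.** Reported rate at time t = compliance among patients due a form × share of randomized patients still due a form. With perfect compliance and no Version 2 stop, this equals the share still on treatment, 0.5^(t/median).

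**Step 2. Planned medians, perfect compliance.** t in months = weeks × 7/30.4375.

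| Time | t (months) | Fulvestrant, 0.5^(t/5.5) | GDC-0810, 0.5^(t/8.5) | Gap (points) |
|---|---|---|---|---|
| Baseline | 0 | 100% | 100% | 0 |
| Week 8 | 1.84 | 79.3% | 86.1% | 6.8 |
| Week 24 | 5.52 | 49.9% | 63.8% | 13.9 |
| Week 48 | 11.04 | 24.9% | 40.6% | 15.8 |

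The gaps come from unrounded rates. At week 24 the rates correspond to about 38 and 49 of 76 patients.

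**Step 3. Dependence on the treatment effect.** Hold fulvestrant at 49.9% at week 24 and set the GDC-0810 rate to 0.499^HR.

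- HR 0.6: 65.9%, a gap of 16.0 points.
- HR 0.8: 57.3%, a gap of 7.4 points.
- HR 1: 49.9%, no gap.

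Extra discontinuation without progression on GDC-0810 would also close the planned gap. The hazard needed is ln2/5.5 − ln2/8.5 = 0.044 per month, or 1 − exp(−0.0445 × 5.52) = about 22% by week 24.

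**Step 4. A reversal.** Suppose compliance at week 24 is 95% on fulvestrant and 85% on GDC-0810. The reported rates are 0.95 × 0.499 = 47.4% and 0.85 × 0.638 = 54.2%, so the arm with better compliance shows the lower figure.

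**Step 5. Version 2.** If collection stops V months after the first patient, the share of patients whose visit at t falls before the stop is min(A, V − t)/A, with A = min(V, 22). At week 24 this is (12 − 5.52)/12 = 0.54 for V = 12 and (26 − 5.52)/22 = 0.93 for V = 26. Week-24 rates become 26.9% versus 34.4% for V = 12 and 46.4% versus 59.4% for V = 26. Both arms are multiplied by the same factor, so the stop lowers the rates without producing a gap.

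**Step 6. With a base of patients due a form.** Perfect compliance gives 100% in both arms at every visit, before or after Version 2.

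**The case against.** The strongest reply has four parts.

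First, the reference to participants randomized to each group may only mean 'by arm', leaving the base unspecified. That reading is possible. But section 6.7 would then give no denominator at all for a rate it intends to compare, and the same clarification would be needed. Likewise, a patient past Version 2 arguably has no assessment point left; the section does not say how she is counted.

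Second, the plan calls the figure completion, not compliance, and an all-randomized percentage fairly describes how much data exist. This stands, and it is a reason to keep that figure under its own label. It does not make the figure suitable for comparing non-response.

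Third, attrition is reported elsewhere: discontinuation by arm (section 6.2), treatment duration (section 6.5) and Kaplan-Meier PFS (section 6.4.1). These give context, but none yields a rate among patients due a form at a given visit.

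Fourth, PROs are exploratory (section 2.4), summarized descriptively and no longer collected, and the visit weeks used here are not taken from a PRO schedule. Section 4.5.8 also does not say that forms were due only during treatment; any form due later would change the shares in the table. All of this stands and limits the weight of the point. It does not repair the definition.

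**Conclusion.** The point holds as a matter of definition and interpretation. After baseline, the stated rate is compliance multiplied by the share of randomized patients still due a form. The arms can therefore differ with perfect compliance, and would under the planned medians: about 50% versus 64% at 24 weeks, given exponential PFS as time on treatment and an illustrative visit time.

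A reader might infer more than the documents support:

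- *That the rate must differ by arm.* It need not. There is no gap at baseline or when time on treatment is equal, and the medians are design assumptions in a trial that section 6.1 describes as hypothesis-generating.
- *That Version 2 produces a difference between arms.* Collection stops in both arms, so in expectation both rates fall by the same factor. Late absolute rates still cannot be read as compliance.
- *That the rate says nothing about compliance, or would necessarily be taken as poor compliance on fulvestrant.* The baseline rate does reflect compliance and later rates contain it; how readers would take a gap cannot be known from the text.

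The effect is confined to the exploratory PRO summaries. Sample size and the primary and secondary analyses are unaffected.

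**What to change.** In section 6.7, define the compared completion rate as completers divided by patients on study treatment and due a questionnaire at that visit under the protocol version in force at the time. Visits after Version 2 took effect then drop out of both numerator and denominator. Report the all-randomized percentage beside it, labelled 'available data', and do not use it to compare non-response. Because Appendices 1 and 2 no longer show a PRO schedule, the text should cite the schedule that applied before Version 2.

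The cost is one or two sentences and one additional denominator in the completion table. No new patient data are needed: the calculation uses treatment dates from the administration eCRFs and the date Version 2 took effect at each site, which the approval records required by section 9.1 should help to establish.

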6.8 ADDITIONAL EXPLORATORY ANALYSES

The analysis of OS will be conducted in all randomized patients. Data for patients who are alive at the time of analysis data cutoff will be censored at the last date they were known to be alive. Data from patients without postbaseline information will be censored at the date of randomization plus 1 day. The OS curve for each treatment arm will be estimated by the Kaplan-Meier methodology, and the hazard ratio and its 90% CI will be estimated by the Cox proportional-hazards model.

Exploratory biomarker analyses may be performed in an effort to understand the association of these markers with study-treatment response.

Whole genome sequencing data will be analyzed in the context of this study and explored in aggregate with other studies to better understand disease pathobiology and guide the development of new therapeutic approaches.

Blood samples may be used for the evaluation of genetic polymorphisms of drug metabolic enzymes, such as CYP3A4/5 and UGT1A1; transporters, such as OATP1B1 and BCRP; and genetic variants, which could contribute to potential drug-safety assessments.

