- Patients experiencing clinical benefit may continue to receive GDC-0810 as a single agent or fulvestrant until progression of disease, unacceptable toxicity, consent withdrawal, GDC-0810 drug supply has been exhausted, or the Sponsor terminates the study.
- Limited physical examination, vital signs, liver function test, creatinine adverse events, concomitant medication, and study drug compliance will be collected at least monthly and as clinically indicated.
- Hematology, ECOG, blood chemistry (except creatinine and liver function tests), urinalysis, bone scans, and CT/MRI scans will be collected per institutional guidelines and as clinically indicated.
- Patient-reported outcome questionnaires will be discontinued.
- Survival information from patients who discontinued from the treatment phase of the study will no longer be collected.
- The IMC will longer be required to monitor ongoing patient safety.
- The Sponsor will continue to monitor clinical safety data in real time.
- No new or potential safety risks have been identified; however, on the basis of accumulated clinical experience, dose modification guidelines have been updated.
- Collection of fasting lipid panel has been removed because it is not essential for ongoing safety monitoring.
- Based on accumulated clinical experience and the addition of elevation of hepatic transaminases as a potential risk in the GDC-0810 Investigator's Brochure, Version 3, Grade ≥ 3 elevation of ALT or AST has been added as adverse event of special interest to align with the other ongoing GDC-0810 study (GO29642).

- Clinical and nonclinical summaries have been update to align with the GDC-0810 Investigator’s Brochure, Version 4.

Note: Exclusion criteria were not updated to align with GDC-0810 Investigator’s Brochure recommendations given discontinuation of study enrollment.

- The definition of the end of study has been revised because of the Sponsor’s decision to halt the development of GDC-0810 (see Section 3.2).
- Post-trial access to GDC-0810 has been revised because of the Sponsor’s decision to halt the development of GDC-0810.

Additional minor changes have been made to improve clarity and consistency. Substantive new information appears in italics. This amendment represents cumulative changes to the original protocol.

TABLE OF CONTENTS

PROTOCOL AMENDMENT ACCEPTANCE FORM	30
PROTOCOL SYNOPSIS	31
1. BACKGROUND	42
1.1 Background on Estrogen Receptor-Positive Breast Cancer.....	42

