2.1 EFFICACY OBJECTIVES

The co-primary efficacy objectives for this study are as follows:

- To evaluate the efficacy of GDC-0810 compared with fulvestrant in the intent-to-treat (ITT) population as measured by PFS
- To evaluate the efficacy of GDC-0810 compared with fulvestrant in patients with detectable *ESR1* mutations as measured by PFS

The secondary efficacy objective for this study is as follows:

- To assess the clinical activity of GDC-0810 versus fulvestrant, as measured by objective response rate (ORR), duration of response (DOR), CBR, and overall survival (OS)

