Enrollment in Study GO29689 has been discontinued; therefore, no further patients will be enrolled in this study. Any patient currently enrolled in Study GO28689 experiencing clinical benefit may continue to receive GDC-0810 as a single agent or fulvestrant until disease progression (as assessed by the investigator based on radiographic findings or clinical symptoms), unmanageable toxicity, patient withdrawal of consent, GDC-0810 drug supply has been exhausted, or the Sponsor terminates the study. All patients who are discontinued from study treatment will return for a study drug discontinuation visit within 30 days after the last dose of study treatment and will be followed for adverse events for at least 28 days after the last dose of study treatment.

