3.4.2 Secondary Efficacy Outcome Measures

The secondary outcome measures for this study are the following:

- OS, defined as the time from randomization to the time of death from any cause
- Objective response (PR plus complete response [CR]) as determined by the investigator per RECIST v1.1 (see [Appendix 7](#))
- DOR, defined as the time from the first occurrence of a documented objective response until first observation of disease progression, as determined by the investigator per RECIST v1.1 (see [Appendix 7](#)), or death from any cause on study, whichever occurs first
- Clinical benefit, defined as PR, CR, or stable disease (SD), lasting for at least 24 weeks from the time of randomization

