A technetium bone scan should be performed at screening (up to 28 days prior to Cycle 1 Day 1) to evaluate for the presence of bone metastases. Positive areas on bone scans should be evaluated by X-ray, CT scan, or MRI prior to randomization (up to 28 days prior to Cycle 1 Day 1). Bone scans should be repeated in the event of clinical suspicion of progression of existing bone lesions, the development of new bone lesions, and in the assessment of a CR, if any disease was evident at screening. For adequate assessment of bone lesions, it is expected that the radiologist will adjust window leveling accordingly.

To ensure a valid comparison of tumor data and uniformity in the assessment of tumor response during the study, the following procedures must be implemented at the study site:

- All lesions identified at baseline (target and non-target) will be reassessed using the same method throughout the course of the study.
- All CT scans and MRIs obtained for all patients enrolled at the center should be reviewed by the local radiologist who, together with the investigator, will determine the local assessment of response and progression. All bone scans obtained from the patients with bone metastases should be reviewed similarly.
- All radiological data (CT scan, MRI and bone scan, etc.) and photos for skin lesions obtained at baseline, during treatment period and the follow-up period must be sent to a central imaging vendor contracted by the Sponsor within 2 weeks of imaging.
- Tumor response and progression will be assessed and will be the basis for the efficacy analyses (along with survival information). The main analysis of the trial will be based on the local radiology review results.

Patients who discontinue study treatment for any reason other than disease progression will continue to undergo tumor response evaluations until progressive disease or initiation of other anti-cancer therapy.

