4.5.11.4 Follow-Up Assessments

All patients will be followed for safety for at least 28 days after the last administration of study therapy. Ongoing adverse events related to study treatment will be followed until the event has resolved to baseline (pretreatment) grade, the event is assessed by the investigator as stable, new anti-tumor treatment is initiated, the patient is lost to follow-up, the patient withdraws consent, or it has been determined that the study treatment or participation is not the cause of the adverse event.

The schedule of follow-up visits and assessments is provided in [Appendix 1](#) and [Appendix 2](#).

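### Section 6.8 was not adapted when Version 2 ended off-treatment survival collection: its open cutoff with last-known-alive censoring can bias the OS curves in either direction

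*Combined protocol and SAP*

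**What the plan says.** The Version 2 amendment rationale states: "Survival information from patients who discontinued from the treatment phase of the study will no longer be collected". This is a rule of the current version, and the current body agrees with it.

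- Section 3.1: patients who stop treatment return for one visit within 30 days and "will be followed for adverse events for at least 28 days after the last dose of study treatment".
- Section 4.5.11.4: "All patients will be followed for safety for at least 28 days after the last administration of study therapy".
- Appendices 1 and 2 have no row for survival contact.
- Section 4.6.2 makes documented progression a reason to stop study drug. Section 3.1 lets patients who are benefiting stay on treatment, and so under observation.
- Section 4.5.5: "Patients who discontinue study treatment for any reason other than disease progression will continue to undergo tumor response evaluations until progressive disease" or the start of other anti-cancer therapy.

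OS nevertheless stays among the secondary outcome measures in Section 3.4.2: "OS, defined as the time from randomization to the time of death from any cause". Section 4.5.5 still names survival data beside tumor assessments as a basis for efficacy. Section 6.8 analyzes OS in all randomized patients; those "alive at the time of analysis data cutoff will be censored at the last date they were known to be alive". It gives the cutoff no date, no event trigger and no link to the end of survival collection. The only event trigger in the plan, about 95 events in Section 6.1, is for PFS.

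**The concern.** Kaplan-Meier and Cox both assume that censoring carries no information about the death hazard. After the stop, patients still on treatment remain in view. Patients who progress leave treatment and drop out of view soon afterwards. Patients already off treatment are last seen near the stop or before it. Later alive-dates for them arise only incidentally, for example from anti-cancer therapy records (footnote f of Appendices 1 and 2) or adverse-event follow-up (Section 5.5.1).

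Two distortions follow, in opposite directions:

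- **Selective loss.** With a cutoff after the stop, the risk set fills with progression-free patients. If death is more likely after progression, the curves are too high.
- **Unequal ascertainment.** If deaths are known up to the stop but living off-treatment patients were last contacted earlier, deaths are counted while the matching time at risk is cut off. The curves are too low, even with the cutoff at the stop.

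At stake are the OS curves of a listed secondary endpoint, which could be reported without a warning.

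**Working it through.** **Design inputs.** The plan gives no OS figure to reproduce. Its PFS precision statement does reproduce: exp(ln 0.6 ± 1.645 × 2/√95) = 0.428 to 0.841, against the stated (0.43, 0.84) in Section 6.1.

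**Inputs from the documents.** PFS medians of 5.5 and 8.5 months and 152 patients (Section 6.1); accrual projected at 22 months (Synopsis, Length of Study).

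**Assumed inputs.** Exponential times; death hazard before progression h0 = 0.004 per month; median survival after progression 12, 18 or 30 months, or no rise in hazard; stop at month 15, 20 or 24; uniform accrual up to the stop (at most 22 months; also 12 months for stop 15 and 14 for stop 20). Patients on treatment at the stop are followed to one month after progression or to the cutoff.

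**True OS.** With λ = ln 2 / median PFS and h1 = ln 2 / median survival after progression:

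S(t) = e^(−λt) + (λ − h0)(e^(−h1·t) − e^(−λt)) / (λ − h1)

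Fulvestrant, post-progression median 12 months: λ = 0.12603, h1 = 0.05776, (λ − h0)/(λ − h1) = 1.78755.

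- S(12) = 0.22040 + 1.78755 × 0.27960 = 0.720
- S(18) = 0.10347 + 1.78755 × 0.25008 = 0.5505

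The simulation (400,000 patients per arm) gives 0.720 and 0.551. For GDC-0810 it gives 0.780 and 0.631.

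**Case A: off-treatment alive-dates current to the stop.** Upward bias in Kaplan-Meier OS at 18 months, across arms and post-progression medians of 12-30 months:

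| Cutoff | Stop 15 | Stop 20 | Stop 24 |
|---|---|---|---|
| At the stop | not estimable | about 0 | about 0 |
| 3 months later | not estimable | 0.01-0.04 | 0.01-0.025 |
| 6 months later | 0.06-0.14 | 0.02-0.06 | 0.01-0.04 |
| 12 months later | 0.06-0.16 | 0.02-0.09 | 0.02-0.06 |

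Example (stop 20, cutoff 26, accrual 20, post-progression median 12), at 12 and 18 months: fulvestrant +0.029 and +0.055; GDC-0810 +0.029 and +0.064. Repeat runs differ by up to about 0.003. If off-treatment status stays visible for 3 months after progression instead of 1, the fulvestrant figures fall to about 0.020 and 0.043. If the hazard does not rise after progression, the bias is 0.00.

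**Case B: off-treatment alive-dates lag the stop by 0-3 months (assumed), deaths known to the stop.** Bias at 18 months, stops at 20 and 24:

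| Cutoff | Bias |
|---|---|
| At the stop | −0.030 to −0.063 (stop 20); −0.013 to −0.029 (stop 24) |
| 3 months later | fulvestrant −0.006 to −0.023 |
| 6 months later | fulvestrant −0.008 to +0.018; GDC-0810 +0.009 to +0.048 |
| 12 months later | +0.001 to +0.079 across arms |

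**Check of the remedy in Case B.** Taking both deaths and alive status at each patient's own last contact leaves +0.011 to +0.036 at 18 months (stop 20). One common date for everyone, 3 months before the stop, leaves at most about 0.002 at 12 months (stops 20 and 24) and at 18 months (stop 24).

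**Scale.** With 76 per arm (152/2) and a 6-month lag, the Kaplan-Meier standard error is 0.04-0.06 at 12 months and 0.05-0.11 at 18 months. The Case A bias is then below one standard error for stops at 20 and 24, but can exceed it at 18 months for a stop at 15.

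**The case against.** The best defense is that Section 6.8 is underspecified, not wrong. Last-known-alive censoring is a standard rule. No section schedules an OS cutoff after the stop, and the PFS cutoff in Section 6.4.1 is undated as well. The sponsor could cut the data at the stop and comply. Enrollment ended early, so standard errors would exceed those for 76 per arm if fewer were enrolled, and the bias would matter less beside the noise.

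Much of this stands, and it keeps the point minor. It does not dispose of it. The standard rule presupposes continuing survival contact, which Version 2 withdrew. Cutting at the stop is safe only if off-treatment alive-dates are current to it, and the documents give no survival-contact interval that would ensure this.

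A reader might infer more than the documents support:

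- **That both OS curves must be too high.** This needs all three conditions of Case A. With lagging alive-dates the sign reverses for a cutoff at the stop and can differ by arm 3-6 months later.
- **That the OS hazard ratio will favor GDC-0810.** In simulation with current alive-dates and a later cutoff, it moved that way by about 0.02-0.07, but only under the assumed PFS advantage. The documents report no PFS result, so no hazard-ratio claim is made.

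**Conclusion.** The concern holds in conditional form, as a minor point. Section 6.8 carries an OS rule written for continuing survival follow-up into a version that ended it.

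- Cutoff after the stop, higher death hazard after progression, current alive-dates: both Kaplan-Meier curves are biased upward. The size is about 0.01-0.06 at 18 months for a 6-month lag with stops at month 20 or 24, and more for an earlier stop or later cutoff.
- Alive-dates behind the stop, deaths known up to it, cutoff at the stop: the curves are biased downward by about 0.01-0.06 at 18 months.
- No rise in hazard after progression and current alive-dates: no bias.

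All sizes are illustrative. The stop date, OS cutoff, number enrolled, currency of alive-dates and post-progression survival are not in the documents. The consequence is limited: Section 6.1 calls the trial hypothesis-generating, Section 2 says the primary objectives will not be met, and no decision in the plan uses OS.

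**What to change.** In Section 6.8, replace last-known-alive censoring at an open cutoff with one common ascertainment date for both deaths and alive status.

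- Set it no later than the date off-treatment survival collection stopped, by site or country if implementation dates differ (Section 9.6 makes implementation depend on local approvals). If status is not complete to that date, use the last earlier date through which it is.
- Censor every patient alive at that date there, and leave later deaths and alive-dates out of this analysis.
- Record the change as post hoc and tied to an administrative date, because Section 5.1 says the study team is already unblinded.
- Label any OS estimate that uses later data as supplementary and subject to informative censoring.

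**Cost.** Wording, a few deaths and the late time points. Per 152 patients under the assumed inputs, a date at the stop loses about 1-3 deaths against a cutoff 6 months later (33.9 − 31.1 = 2.8 in the example) and about 2-5 against one 12 months later. For a stop at month 15, 18-month OS cannot be estimated. Moving the date back 3 months loses a further 5-12 deaths for stops at 20 and 24 (31.1 − 21.5 = 9.6 in the example), and 18-month OS is then also lost for a stop at 20. If that is too much, state that OS will not be estimated and report only deaths on treatment and within 28 days of the last dose.
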